### 3.1 Participants.

**Table 1 Eligibility Criteria**

Inclusion Criteria	Exclusion Criteria

 
✓ women aged 21 years and older
 
✓ diagnosis of ovarian cancer, stages I to IV
 
✓ have average persistent fatigue defined as <math>\geq 4</math> on the Brief Fatigue Inventory
 
✓ fatigue must have started at or after the diagnosis of ovarian cancer
 
✓ initiated all primary cancer treatments (surgery, chemotherapy at least 3 weeks prior), including maintenance therapies
 
✓ undergone any primary debulking surgery at least 4 weeks prior
 
✓ undergone interval debulking surgery at least 4 weeks prior if they have had neoadjuvant chemotherapy (NACT)
 
✓ no other planned interventions for fatigue other than current stable medication
 
	
 
✗ medically unstable
 
✗ acupuncture or acupressure receipt in past year
 
✗ have a diagnosis of untreated mood disorder, e.g., bipolar or major depressive disorder
 
✗ have a current diagnosis of anemia
 
✗ have a current untreated diagnosis of hypothyroidism
 
✗ have an initiation, a cessation or change of treatment of any chronic medications, dietary supplements, behavioral therapy, physical therapy etc., or any planned change of medications, supplements or therapies during the study
 
✗ have the possibility of becoming pregnant
 
✗ diagnosis of COVID-19 on or after 3/1/2020 with fatigue onset following diagnosis
 

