## 1.0 BACKGROUND AND SIGNIFICANCE

**Fatigue and Ovarian Cancer.** Women diagnosed with ovarian carcinoma (cancer) report multiple quality of life challenges, including persistent fatigue and sleep disturbances. Persistent fatigue is a commonly reported symptom in these women, with as many as 30 to 60% of ovarian cancer survivors continuing to report significant fatigue even several years after the end of treatment. In ovarian cancer, persistent fatigue has been linked to higher levels of chronic pain, lower quality of life, and reduced participation in other self-care activities such as physical activity. Interestingly, risk factors for fatigue post cancer treatment does not appear to be associated with type of cancer, cancer treatment, stage of diagnosis or histopathology of the cancer, but instead with other host factors such as presence of depression or level of physical activity. While the etiology of persistent fatigue in cancer survivors is unknown, recent research in female cancer survivors suggests that cancer related fatigue may involve pathology within the brain, and thus treatments that target the brain may have promise for treating fatigue. Despite the challenges caused by persistent fatigue, there have been very limited attempts to identify self-care-focused interventions, which could improve fatigue, sleep, and quality of life among ovarian cancer survivors. We are proposing to carry out a randomized, controlled trial comparing self-administered acupressure to sham acupressure and no treatment to determine if this is an intervention that survivors can use to address their fatigue.

[figure not shown]

**Figure 1.** A plot of mean weekly fatigue scores for relaxing acupressure (red circles), High Intensity Stimulating Acupressure (closed black circles), and Low Intensity Stimulating (open circles) across study weeks

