### Acupressure and Fatigue

Self-administered acupressure is one possible safe, self-management technique for improving persistent fatigue as well as physical and psychosocial functioning in ovarian cancer survivors with chronic cancer-related fatigue. Acupressure, a technique derived from acupuncture, is a component of Traditional Chinese Medicine in which pressure is applied to specific acupoints on the body using a finger or small device to address health issues. Acupressure has shown promise for treating fatigue in cancer patients and survivors, although these have been small studies with numerous methodological flaws including inclusion of multimodal treatment approaches, patients currently receiving or recently completing cancer treatment, and no examination of carry-over effect of acupressure. We performed a pilot intervention of relaxing and stimulating self-acupressure in fatigued adult cancer survivors, of which 14% had been diagnosed with ovarian cancer. In this study, participants were randomized to one of three groups: 1. relaxing acupressure ( $n=14$ ); 2. High intensity stimulating acupressure ( $n=15$ ); or 3. low intensity stimulating acupressure ( $n=14$ ). Participants performed acupressure for 12 weeks between 3 to 14 times per

**Figure 2.** Scatter plot of individual participant BFI change scores (week 12—week 0) indicate greater reductions for relaxing acupressure (red circles), High Intensity Stimulating Acupressure (closed black circles), and Low Intensity Stimulating (open circles).

accuracy with which the acupressure treatment was performed by participants including correct location of acupoints, amount of pressure, duration and frequency of treatments (95% out of 100% on their fidelity ratings), and adherence (performed 73% of all acupressure sessions on average). **These data indicate that acupressure was effective in reducing fatigue in female cancer survivors, and importantly, survivors can be recruited through the Michigan Cancer Registry and a large randomized, controlled study completed. However, no study has examined using a mobile app to teach female cancer survivors to self-administer acupressure — an important innovation to help increase implementation and accessibility for cancer survivors.**

[figure not shown]

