### **3.2 Randomization.**

The biostatistician will provide sealed envelopes for the randomization of all participants. Participants will be

randomized to one of the three study arms: Acupressure, Sham acupressure or Control. A random generator for block stratified randomization in blocks of 6 participants will be programmed by [name], the study statistician. Eligible patients will be randomized into one of three groups - relaxing acupressure, sham acupressure, or no treatment - in a 1:1:1 ratio for a total of 171 participants with 57 randomized into each group.

We will be delivering our self-acupressure interventions (relaxing and sham) using our modified MeTime Acupressure mobile app. We will rename the MeTime Acupressure app to "Study App" and change the icon so participants will not be able to locate it in the Apple or Google Play Stores and unblind themselves. In association with the 3D Media Lab at the University of Michigan we will create a mobile app for our sham acupressure points. The sham and relaxing acupressure apps will be identical in all aspects except for the acupoint locations. For women randomized into the "no treatment arm" they will receive the acupressure app and AcuWand at the end of their study participation. The acupressure app will be loaded onto computer tablets by our computer information technology (IT) support person. Women in the acupressure arms will also receive an AcuWand to be used in association with the acupressure app to help women apply the correct amount of pressure to acupoints. The women will receive directions within the acupressure app on how to use the AcuWand. The AcuWand has been designed to use two lithium-ion long lasting (up to one year with normal use) batteries. Participants are asked to return the AcuWand with provided materials at no cost to them in order to upload data about frequency, duration and amount of pressure of acupressure applications. Of note: no Wi-Fi connection is needed to use the acupressure app and our IT support person will be available to help participants who are unfamiliar with or have any issues with their tablet, AcuWand or the app.

**Relaxing Acupressure.** There are 5 acupoints with 4 of the acupoints performed on both the left and right sides of the body (total of 9 points to stimulate; see Figure 7). Each of the 9 acupoints will be stimulated for 3 minutes per point

with the AcuWand giving a total treatment time of 27 minutes daily. The relaxation acupoints are:

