**Table 2**

	Screening phone call	Baseline Week 0	Treatment Phase Weeks 1 - 6	Follow-up Week 6 (- 2 days/+5 days)	Follow-up Week 12 (- 2 days/+5 days)	Follow-up Week 24 (- 2 days/+5 days)
Phone Screen	X					
Screening Survey	X					
BFI	X	X		X	X	X
PHQ-2	X					
Consent	X					
Pt. Info & Dem.	X					
Concomitant of Medications		X				
Diagnosis & Treatment of initial cancer		X				
FACT-O		X		X	X	X
PSQI		X		X	X	X
PROMIS		X		X	X	X
IPAQ		X				
SCQ		X				
FSQ		X				
MAIA		X		X		
Daily Logbook			X			
Acupressure Fidelity				X		
Assessment of blinding				X		
AcuWand Comfort				X		
Final Evaluation						X

**Administering Study Assessments.** All potential participants will be screened over the phone using a brief questionnaire to confirm eligibility for the study. Enrolled participants will then receive an email link to their RedCAP study measures at baseline, weeks 0, 6, 12 and 24. All the surveys will be administered at all-time points with the exception of descriptive and baseline assessments, which will only be collected at week 0; fidelity, blinding and adherence, which will only be asked at week 6; and a final evaluative questionnaire about the participants' perception of the study and the use of the AcuWand device. Adverse events will be collected at all-time points. Inspirational reminder emails, texts, or phone calls (as appropriate for a given participant) will be made to encourage the highest possible response rate to each round of study assessments. Participants without an email account will be assisted in obtaining a free Gmail account and how to access it on their computer tablet by study staff. Those participants who do not have access to Wi-Fi will be assisted in finding free Wi-Fi in their community (e.g., public library, Starbucks, McDonalds, etc.) IT study staff will be available to assist participants with any questions that may arise. E-mail is required so that study instruments may be accessed through surveys in RedCAP.

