**Screening.** All potential participants will be screened over the phone using a basic questionnaire to confirm their eligibility. Specifically, an abbreviated form of the *Patient Health Questionnaire (PHQ-2)* will be used to detect untreated depression, and the *Brief Fatigue Index (below; BFI)* will be used to determine fatigue. These measures will be collected before consent and enrollment in to the study and will therefore be kept to the absolute minimum to determine eligibility.

Rescreening. Participants may be rescreened at 6 weeks after initial screening if they failed their initial screening based on: stable chronic medications and no new planned interventions for their fatigue or cancer.

**Fatigue Measure (administered at screening and weeks 0, 6, 12, 24).** *Brief Fatigue Inventory (BFI)* will be used to assess the severity and impact of fatigue on daily functioning. The BFI is a scale validated in cancer patients with an alpha coefficient exceeding 0.95, which correlates well with other fatigue measures. The BFI assesses severity and impact of fatigue in cancer patients over the past 24 hours. The instrument consists of 9 items, each measuring fatigue on a 0-10 scale, and is calculated from the mean of completed items. Scores of  $\geq 4$  indicate clinically- relevant fatigue. A three-point change or a drop below 4 is considered a clinically meaningful change.

**Sleep Quality (administered weeks 0, 6, 12, 24).** *Pittsburgh Sleep Quality Index (PSQI)* is widely used 19-item questionnaire evaluates sleep disturbance over the past month. It yields a total score and 7 component scores: sleep quality; sleep latency; sleep duration; habitual sleep efficiency; sleep disturbances; use of sleep-promoting medication; and daytime dysfunction. In women with breast cancer, Cronbach's alpha for the global PSQI is 0.80. A score  $>7$  in breast cancer patients and thus likely in ovarian cancer patients suggests poor sleep quality. The scale has adequate psychometrics. The primary outcome will be the total PSQI score at baseline and week 6, although we will conduct exploratory analyses on the PSQI subscales.

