### Statistics Section.

The primary aim of this study is to investigate the differential effects of different modes of acupressure (relaxing vs. sham vs. no treatment) on fatigue as measured by the BFI in ovarian cancer survivors at week 6. The BFI, which measures the average degree of fatigue, gives a score that ranges between 0 and 10, with higher numbers indicating more fatigue. To investigate the difference in BFI between the three study arms, we shall use linear mixed-effects regression analysis with BFI as outcome, *week* as the within-subjects factor with four levels (0, 6, 12, 24) and *group* (relaxing acupressure, sham acupressure, no treatment) as the primary between-subjects factor. Of interest is the group-by-week interaction (to be included in the model), significance of which will indicate differences in extent of decrease between the arms. The covariate cancer stage at diagnosis and the interaction term group-by-stage will be added to models. Post-hoc sliced main effect of weeks within each study arm will be estimated. A *subject* random-effect will be used to account for the clustering effect within the four measurements on the same subject. Model diagnostics will be carried out to confirm the distributional assumptions and appropriate corrective actions (e.g. transformation) will be performed as needed. Models with more flexible covariance pattern (e.g. unstructured covariance, heterogeneity across groups) will be explored. An additional analysis with a spline version of weeks will be carried out which uses *week* as a continuous variable allowing one to estimate the rate of change in BFI.

A secondary analysis with BFI will also be carried out which investigates the difference in proportion of fatigued subjects ( $BFI \geq 4$ ) across the three study arms. The analytical framework will be that of a mixed-effects logistic regression model with presence of fatigue ( $BFI \geq 4$  yes/no) being the dichotomous outcome. Apart from group, week, and group-by-week interaction as primary covariates, the model will also be adjusted for baseline status of severity. Remaining covariates in the model are identical to those in the continuous BFI model. The clustering effect due to subject will be accounted for using a generalized estimating equations approach under a generalized linear mixed models framework.

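### Women still on chemotherapy or maintenance can enter this survivor trial, but the BFI model adjusts for stage at diagnosis and not for current treatment status

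*Combined protocol and SAP*

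**What the plan says.** **Eligibility.** Table 1 (section 3.1) includes women who have "initiated all primary cancer treatments (surgery, chemotherapy at least 3 weeks prior), including maintenance therapies", and sets a minimum of 4 weeks since debulking surgery. No line requires treatment to be complete. Another line of Table 1 excludes "any planned change of medications, supplements or therapies during the study". The rescreening paragraph in section 4.1 names as screening conditions "stable chronic medications and no new planned interventions for their fatigue or cancer".

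**Target population.** The aims speak of persistent fatigue in ovarian cancer survivors. Section 1.0 describes survivors "continuing to report significant fatigue even several years after the end of treatment". Under Acupressure and Fatigue, the methodological flaws attributed to earlier studies include enrolling "patients currently receiving or recently completing cancer treatment".

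**Allocation and analysis.** Section 3.2 describes "block stratified randomization in blocks of 6 participants" and names no stratification factor. For the BFI model, the Statistics Section says "The covariate cancer stage at diagnosis and the interaction term group-by-stage will be added to models". Current cancer treatment appears in neither place.

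**Data collected.** Table 2 has a week-0 row for "Diagnosis & Treatment of initial cancer". The descriptive variables in section 4.1 also cover cancer treatments and diagnoses, cross-checked against the tumor registry, and concomitant medications with dose, duration and reason. Section 6.2 documents chronic medications during the study. The background reports that the pilot's group difference in BFI change was adjusted for cancer treatments, among other covariates.

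**The concern.** Fatigue in a woman receiving chemotherapy may change over six weeks for reasons that have nothing to do with acupressure, and the BFI asks only about the past 24 hours. If such women are mixed with women long past treatment, and the model does not know which is which, three things follow.

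- The spread of the week-6 change grows, which weakens every contrast. Relaxing versus sham has least to spare.
- The share on treatment can differ between arms by chance and move the estimated difference in either direction.
- A positive result cannot readily be assigned to post-treatment survivors, the group that the background describes.

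Stage at diagnosis does not fill the gap, because it does not say whether a woman is on treatment now.

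**Working it through.** **Inputs from the plan.** Section 9.0 assumes a baseline BFI of 5.5 and end-of-treatment means of 4.5 (no treatment), 3.5 (sham) and 2 (relaxing), so the changes are -1, -2 and -3.5. It assumes 50 evaluable women per arm, two variance components of 4 each and an intra-class correlation of 0.5. The variance of the change can be read in two ways:

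- the second component is the residual: 2 x 4 = 8;
- the total variance is 4: 2 x 4 x (1 - 0.5) = 4.

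Section 9.2 gives a third value, from a pooled SD of 1.7: 1.7² = 2.89.

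**Inputs assumed.** The documents do not give the share p on chemotherapy or the difference d in mean BFI change between women on and off it. The illustration uses p = 0.3 and d = 1.5. The range is p = 0.2 to 0.5 and d = 1 to 2.

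**Step 1: the plan's own figure.** The squared deviations of the three changes from their mean sum to 3.167. The noncentrality is 50 x 3.167 / 8 = 19.8. A noncentral F with 2 and 147 degrees of freedom at 5% gives power of 98.2%; with variance 4 it exceeds 99.9%. The stated figure of more than 95% is reproduced.

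**Step 2: variance added by leaving status out.** This is p(1 - p)d² = 0.3 x 0.7 x 1.5² = 0.47.

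| Variance of change | Added share, p = 0.3, d = 1.5 | Standard error rises by | Added share over the range |
|---|---|---|---|
| 8 | 6% | 3% | 2% to 12.5% |
| 4 | 12% | 6% | 4% to 25% |
| 2.89 | 16% | 8% | 6% to 35% |

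**Step 3: power after the increase.** The relaxing-versus-sham column takes a difference of 3.5 - 2 = 1.5 in week-6 change, 50 per arm, the 0.01 level and a normal approximation.

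| Variance of change | Overall test at 5% | Relaxing vs sham at 0.01 |
|---|---|---|
| 8, status ignored in planning | 98.2% | 53% |
| 8 + 0.47 | 97.7% | 50% |
| 8.16 to 9.0 (range) | 98.1% to 96.9% | 52% to 47% |
| 4, status ignored in planning | above 99.9% | 88% |
| 4 + 0.47 | above 99.9% | 83% |
| 4.16 to 5.0 (range) | 99.9% or more | 86% to 78% |

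The pairwise starting values fall short of the more than 90% stated in section 9.0. That is a separate matter; only the drop from each starting value belongs to this point.

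**Step 4: chance imbalance.** The resulting shift in a two-arm contrast has SD d x sqrt(2p(1 - p)/50) = 1.5 x sqrt(0.42/50) = 0.14 BFI points, or 0.08 to 0.20 over the range. This is the added variance of step 2 seen another way (0.4725 x 2/50 = 0.0189 = 0.137²), so the two must not be added together. For scale, Table 4 shows a true-versus-sham difference of 0.66, and 0.14/0.66 is about a fifth of it.

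**Step 5: which model term helps.** With a subject random effect, a status main effect shifts a woman's level at every visit and does little for her change from baseline. Status-by-week is the term that removes the added variance from the week-6 change.

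**The case against.** **Survivor is not defined as treatment completed.** The objectives accept women whose fatigue began at or after diagnosis, which fits Table 1, and the remark about fatigue years later describes how long it can last. This stands: admitting women on treatment is a design choice. It still sits awkwardly with the flaw named in the background, and section 4.0 does not justify it.

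**A reader might infer that Table 1 contradicts itself.** It does not. Inclusion and exclusion lines apply together. A woman on unchanged maintenance can meet both, and one with a planned change of therapy is excluded. What remains is an ambiguity: whether cancer treatment due to end or change within the 25 weeks is a planned change.

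**A reader might infer bias, for example that chemotherapy ending during weeks 6 to 24 creates a false lasting effect.** The documents do not support that. The sham and no-treatment arms are randomised and concurrent, so such courses balance in expectation. Read literally, the exclusion also removes women whose treatment is due to end in that time.

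**A reader might infer from Table 2 that only treatment of the first cancer is recorded, once.** Section 4.1 describes broader baseline collection and section 6.2 covers medications during the study. A limit remains: section 6.2 counts only medicines used for at least 14 days continuously, so intermittent infusions may escape it.

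**Size and prognostic strength are assumed.** This is fair. Section 1.0 says fatigue is not linked to type of treatment, but that concerns fatigue after treatment, not during it. In addition, if the data in section 9.2 come from this trial, any mixing is already inside 2.89, and adding 0.47 to it counts it twice.

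**It may be too late.** Section 9.2 and Tables 3 and 4 report week-6 changes for 137 women in matching arms, without naming the source. If they are from this trial, new eligibility wording or a new stratum would reach few women or none, and an added analysis could not be called prespecified. That is why the fix centres on the analysis.

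**Conclusion.** The point holds as one of precision and interpretation. Women on current cancer treatment can enter, and the BFI model ignores their status although the plan collects treatment data at baseline and the group's pilot adjusted for it. The unnamed factor in section 3.2 leaves stratification by treatment status unspecified; it does not show that it is absent.

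Under the assumed 30% and 1.5 points, the variance of change rises by 6% to 16%, according to which of the plan's variances is used, and the standard error by 3% to 8%. Overall power stays above 95% across the whole assumed range. Relaxing versus sham at 0.01 loses about 3 to 5 percentage points in the illustration and up to about 10 at the extreme of the range. These sizes rest on a prevalence and a difference that the documents do not give. The attribution problem does not depend on the size of d: without results by treatment status, the reader cannot tell whether the finding applies to women past treatment.

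**What to change.** 1. Derive baseline anticancer treatment status (none, maintenance, chemotherapy) from the baseline treatment and medication data. Check first that the forms capture current treatment, given the Table 2 label. Add status and status-by-week to the BFI model, next to stage at diagnosis or in its place.
2. Report the week-6 contrasts for women not on chemotherapy as a supportive analysis. Label it post hoc if the data in section 9.2 and Tables 3 and 4 come from this trial.
3. Reconcile the inclusion line on treatment begun with the exclusion for planned changes, so that it is clear whether a scheduled end of cancer therapy counts as a planned change. Which rule is right is for the sponsor and investigators.

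**Cost.** With three status levels and four visits, the model spends 2 + 2 x 3 = 8 degrees of freedom, or 1 + 3 = 4 with two levels, against about 3 x (150 - 3) = 441 for error. The supportive analysis is less precise: with 30% removed, 35 women per arm remain and the standard error is sqrt(50/35) = 1.20 times as large if the spread is unchanged, so it supports interpretation and should not be a second test of the primary aim. Items 1 and 2 should need no new data if current treatment proves to be on the forms. Item 3 is a wording change and helps only women still to be screened.
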